**Investigational Agent:**

Drug Name:	Avelumab
IND Number:	130884
Sponsor:	Center for Cancer Research
Manufacturer:	EMD Serono

**Commercial Agents:** None

## **PRÉCIS**

### **Background**

- Recurrent respiratory papillomatosis (RRP) is a rare papillomatous disease of the aerodigestive tract that is caused by the Human Papilloma Virus (HPV).
- RRP can progress to cause airway compromise, fatal pulmonary lesions, and invasive cancers.
- There is no effective systemic therapy for RRP. Patients require repeated interventional procedures for disease control.
- Study of a small number of RRP samples has shown PD-L1 expression by inflammatory mononuclear cells and by papilloma epithelial cells.
- This clinical trial will evaluate the activity of a PD-L1-targeted drug, avelumab, in the treatment of RRP. This drug was selected for its demonstrated activity in a variety of cancers and for its acceptable safety profile.

### **Objective**

- Determine the complete response rate for avelumab in the treatment of patients with RRP.

### **Eligibility**

- Histologically confirmed diagnosis of RRP.
- One of the following:
  - A Derkay anatomic score of 10 or greater and a history of two or more endoscopic interventions in the last 12 months for control of RRP.
  - Pulmonary RRP with pulmonary disease that is measurable by computed tomography scan.
  - Tracheal involvement with RRP that has required either two or more endoscopic interventions in the last 12 months or a tracheostomy.
- Age 18 years or greater.
- Eastern Oncology Cooperative Group Performance Score of 0 or 1.

### **Design**

- Phase II clinical trial
- Simon optimal two-stage design with initial enrollment of 12 patients and expansion to 37 patients if one or more complete response(s) is/are observed in the initial patients.

## **1 INTRODUCTION**

### **1.1 STUDY OBJECTIVES**

#### 1.1.1 Primary Objective

To determine the complete response rate for avelumab in the treatment of patients with recurrent respiratory papillomatosis (RRP).

#### 1.1.2 Secondary Objectives

- Exploratory analyses to assess:
  - PD-L1 expression as a potential biomarker of response.
  - HPV type as a potential biomarker of response.
  - Induction of HPV-specific T cells responses.
  - Clearance of HPV infection from normal appearing mucosa.
- Determine the effect of treatment with avelumab on Derkey and Voice Handicap Index-10 scores.
- Determine the partial response rate for avelumab
- Determine the duration of clinical responses to avelumab

### **1.2 BACKGROUND AND RATIONALE**

#### 1.2.1 Recurrent respiratory papillomatosis (RRP)

RRP is a rare but difficult-to-treat and sometimes fatal neoplastic disease of the aerodigestive tract. RRP is caused by infection with human papillomavirus (HPV) type 6 or 11, or more rarely type 16 [1]. Approximately 1,500 new cases of RRP are diagnosed each year in the United States [2]. RRP is classified based on age of onset as juvenile or adult. Juvenile-onset disease has an incidence of 4/100,000 and tends to have an aggressive clinical course. Adult-onset RRP has an incidence of 2-3/100,000 and tends to have a more indolent clinical course. RRP morbidity and mortality results from papilloma mass effects on the vocal cords, airways, or lungs. This may cause voice changes, stridor, airway occlusion, loss of lung volume, and/or pneumonia [3]. Repeated procedures are required to debulk and monitor the disease, which exposes patients to anesthetic and surgical risk, and emotional distress. It is estimated that the economic cost of RRP is \$150M in the United States each year [2]. Although rare (one to three percent of cases) RRP can transform into invasive squamous cell carcinoma [4]. Subsequent mortality is based upon the clinical stage of the malignancy at the time of diagnosis.

[figure not shown]
There is no cure for RRP. The mainstay of treatment is endoscopic debulking with ablation or excision of papillomatous lesions. Surgical principles dictate that, to minimize morbidity from treatment, papillomatous disease but not normal appearing epithelium is removed. It is thought that latent HPV viral particles persistent in an inactive state in the clinically-normal mucosa and subsequently become reactivated leading to RRP recurrence [5]. Patients with juvenile-onset RRP require on average 20 surgeries over their lifetime to control their disease [6]. Patients with adult-onset RRP generally require fewer interventions; nonetheless greater than 50% will require 5 or more procedures to control symptoms [7]. Adjuvant systemic therapies have been tested in clinical trials, including systemic interferon- $\alpha$  and local injection of anti-viral and antiangiogenic

agents [5]. Study results have been inconsistent, and no single adjuvant approach has been widely adopted or accepted as the standard of care.

### 1.2.2 Avelumab

Avelumab is a fully human monoclonal antibody (HuMAb; immunoglobulin G1 [IgG1]) that targets programmed death-ligand 1 (PD-L1). Programmed death-1 (PD-1) is a negative regulatory molecule expressed by activated T and B lymphocytes. Binding of PD-1 to its ligand, PD-L1, results in the down-regulation of lymphocyte activation (**Figure 1**). Inhibition of the interaction between PD-1 and PD-L1 promotes activation of adaptive immunity and antigen-specific T-cell responses to both foreign antigens as well as self-antigens. Avelumab is produced using standard mammalian cell cultivation and chromatographic purification technologies.

**Figure 1**

Nature Reviews | Cancer

Pardoll, *Nat Rev Cancer*, 2012

The clinical use of monoclonal antibodies that block T-cell inhibitory receptors has provided transformative information on the nature of the immune system and cancer. An emerging picture suggests that endogenous immune responses can mediate effective tumor regression and/or improved survival even in patients with large volume tumors resistant to other forms of therapy. Some of the unique features of this type of therapy, based largely on experience in advanced melanoma, include: improved overall survival (OS) with or without radiographic responses or improved progression-free survival (PFS); responses that may be delayed or occur after radiographic disease progression; combinations of immune modulators with enhanced or novel activities (in the example of anti-CTLA4 and anti-PD-1 agents); and toxicity that is almost exclusively immune or inflammatory in nature. It is not yet clear what factors determine

responses and which components of the immune system are needed for this to occur. It seems likely that both memory helper and effector cells would be needed to sustain long-term responses. Increasing emphasis has been placed on understanding the relationships of the tumor, cellular infiltrate, and immunologic milieu surrounding each tumor.

PD-1, a 55-kDa type 1 transmembrane protein, is a member of the CD28 family of T-cell co-stimulatory receptors that include Ig super family member CD28, CTLA-4, inducible co-stimulator (ICOS), and B and T lymphocyte attenuator (BTLA).[8] PD-1 is transiently but highly expressed on activated T cells functioning to limit immune effectors at the site of activation. Chronic stimulation may prevent the re-methylation of the PD-1 gene leading to continuous expression and characterizes a state of “exhausted” T cells that lose function and proliferative capacity while enhancing a suppressive tumor microenvironment. PD-1 may act together with other T-cell modulating molecules, including CTLA-4, TIM-3, lymphocyte-activation gene 3 (LAG-3) as well as indoleamine-pyrrole 2,3-dioxygenase 1 (IDO-1), cytokines, and transforming growth factor beta (TGF-beta).

Two ligands specific for PD-1 have been identified: PD-ligand 1 (PD-L1, also known as B7-H1 or CD274, expressed on tumor, antigen-presenting cells [APCs], and dendritic cells [DCs]) and PD-L2 (also known as B7-DC or CD273, expressed on endothelial cells). The interaction of PD-1 with PD-L1 and PD-L2 results in negative regulatory stimuli that down-modulate the activated T-cell immune response through SHP-1 phosphatase.

PD-1 knockout mice develop strain-specific lupus-like glomerulonephritis (C57BL/6) and cardiomyopathy (BALB/c). In transplantable tumor models that expressed PD-1 and LAG-3 on tumor-infiltrating CD4+ and CD8+ T cells dual anti-LAG-3/anti-PD-1 antibody treatment cured most mice of established tumors that were largely resistant to single antibody treatment.[9] Despite minimal immunopathologic sequelae in PD-1 and LAG-3 single knockout mice, dual knockout mice abrogated self-tolerance with resultant autoimmune infiltrates in multiple organs, leading to eventual lethality.

PD-L1 expression is found on a number of tumors, and is associated with poor prognoses based on OS in many tumors, including melanoma,[10] renal,[11-13] bladder, esophageal,[14] gastric,[15] ovarian,[16] pancreatic,[17] lung,[18] and other cancers.[8]

The PD-1/PD-L1 axis plays a role in human infections, particularly in hepatitis C virus (HCV) and human immunodeficiency virus (HIV). In these cases, high expression levels of PD-1 were found in viral-specific CD8+ T cells that also display a non-responsive or exhausted phenotype. Non-responsive PD-1-high T cells were observed in simian immunodeficiency virus (SIV) infection in rhesus macaques. Treatment of SIV-infected macaques with an anti-PD-1 mAb (3 mg/kg x4) resulted in decreased viral loads and increased survival along with expanded T cells with increased T-cell functionality.

#### 1.2.2.1 Nonclinical Development of Avelumab

In intravenous (IV) repeat-dose toxicology studies in cynomolgus monkeys, avelumab alone was well tolerated (change this reference to the avelumab IB)[8]. Avelumab bound specifically to monkey PD-L1 with an affinity constant of 1.1 nM. In monkeys, a no-observed-adverse-effect-level was observed at a dose of avelumab significantly higher (140 mg/ml) than that selected for clinical development (10 mg/ml). Avelumab monotherapy increased survival time in MC38

(colon carcinoma) and PANC02 (pancreas adenocarcinoma) tumor-bearing mice in a CD8 T-cell dependent fashion and appeared to induce NK-cell mediated antibody dependent cellular cytotoxicity in some tumors.

#### 1.2.2.2 Clinical Development of avelumab

Avelumab is an investigational fully-human monoclonal antibody (IgG1) that specifically targets PD-L1. It has demonstrated clinical activity in a variety of solid tumor types including NSCLC, merkel-cell carcinoma, gastric, ovarian and bladder cancer. Similar to other checkpoint inhibitors, many responses have been durable lasting beyond the duration of active therapy. Over 700 patients have been treated in initial MTD and expansion cohort phase I trials, with a phase II trial in metastatic merkel-cell carcinoma and a phase III trial in recurrent NSCLC underway. The clinical activity and safety information presented here focuses primarily on data obtained from EMR100070-001 (Phase I, open label trial in primarily Caucasian patients) and MER100070-002 (Phase I, open label trial in Asian patients).

Nine of 53 (16.9%) initial patients experienced  $\geq$  grade 3 AEs potentially related to avelumab including immune-related AEs. None of the subjects treated with doses up to 10 mg/kg experienced a DLT, thus 10 mg/kg q2 weeks dose of avelumab was considered a safe and well-tolerated dose for further investigation in the expansion cohorts

### 1.2.2.3 Pharmacokinetics

Pharmacokinetics (PK) of avelumab was linear in the range of 1 to 20 mg/kg, with dose-proportional increases in maximum serum concentration ( $C_{max}$ ) and area under the concentration-time curve from time zero to infinity ( $AUC_{0-\infty}$ ), with low to moderate inter-subject variability observed at each dose level (insert avelumab IB here)[8]. Clearance of avelumab is independent of dose in the dose range (1-20 mg/kg). Body weight normalized dosing showed approximately constant trough concentrations over a wide range of body weights. The mean terminal elimination half-life of avelumab is 5 days.

### 1.2.3 PD-1-targeted therapy for RRP

[figure not shown]
RRP is caused by HPV infection. HPV infections are common, but most individuals clear the virus without manifesting papillomas, dysplasia, or invasive cancers [19]. Why some immunocompetent individuals are unable to eliminate the virus and therefore develop papillomatosis is not understood. Local therapies fail to eradicate the disease apparently due to chronic persistence of latent virus in normal appearing mucosa. This notion is supported by a study demonstrating the presence of HPV DNA in the clinically healthy mucosa of patients with RRP [20].[21][21][21]. Efforts to study systemic immunotherapy for RRP have been limited. Adjuvant IFN- $\alpha$  after papilloma treatment was shown to increase short-term time to recurrence but did not demonstrate long-term benefit [22].

Clinical trials with new immunotherapeutic agents such as checkpoint inhibitors that block the cytotoxic T-lymphocyte-associated antigen 4 (CTLA-4), or programmed cell death 1 (PD-1) receptors or their ligands such as PD-L1, have not been reported for the treatment of RRP. PD-1 expression has been observed by flow cytometric analysis of T cells infiltrating respiratory papillomas, and PD-L1 mRNA expression in papillomas has been observed by RT-PCR [23]. Study of a small number of RRP samples by our group has shown PD-L1 expression by inflammatory mononuclear cells and by papilloma epithelial cells (**Table 1** and **Figure 2**). Expression of PD-L1 by tumor-infiltrating immune cells or by the tumor cells themselves has positively correlated with tumor response in clinical trials of drugs PD-1/PD-L1-targeted drugs [24]. This clinical trial will evaluate the activity of a PD-L1-targeted drug, avelumab, in the treatment of RRP. This drug was selected for its demonstrated activity in a variety of cancers and for its acceptable safety profile.

**Table 1 PD-L1 expression on RRP**

	N (30 samples tested)	%
Epithelial cell membranous or infiltrating hematopoietic cells	24	80
Epithelial cell membranous	18	60
Infiltrating hematopoietic cell	22	73
Epithelial cell membranous and infiltrating hematopoietic cells	16	53

**Figure 2**

**PD-L1 expression by a respiratory papilloma.** Blue arrows point to mononuclear inflammatory cells demonstrating strong PD-L1 expression on their surface. Purple arrows point to squamous epithelium of the papilloma with PD-L1 expression. 200x, original magnification.

#### 1.2.4 Summary of risks and potential benefits

This clinical trial is being performed to evaluate avelumab for RRP. Only patients with a substantial disease burden (Derkey anatomic score of 10 or greater) that requires repeated endoscopic interventions (two or more procedures in the last 12 months) will be eligible for treatment. While the vast majority of patients with RRP experience an acceptable level of disease control with infrequent surgical debulking, a small subset of patients have very aggressive disease that requires frequent operative intervention, carries the risk of airway obstruction and the need for a tracheostomy, and affects their voice and breathing to a degree that negatively impacts their quality of life. The inclusion criteria for this study captures these 5-10% of patients most severely affected. Patients with disease that has not met this level of severity will not be subjected to the risks of treatment. The primary protocol risks are the toxicities of avelumab. There may be additional risks of treatment that are specific to RRP such as swelling or progression of papillomas that may lead to worsening symptoms. In addition, there are risks from the general anesthesia and procedures to stage and monitor the disease. General anesthesia will be employed during an initial evaluation to stage the disease, confirm the diagnosis, and debulk papillomas that pose an undue safety risk. It will be used again two weeks after the initiation of treatment at which time the airway will be assessed for safety. A final procedure under anesthesia will be performed at the completion of treatment to remove residual papillomas if they are present. Rare but serious complications can occur with general anesthesia including cardiopulmonary compromise, stroke, and death. In this protocol they are offset substantially by the important safety information related to airway patency, extent of disease, and in some cases surgical removal of disease that is gained by these procedures.

## **2 ELIGIBILITY ASSESSMENT AND ENROLLMENT**

### **2.1 ELIGIBILITY CRITERIA**

#### 2.1.1 Inclusion Criteria

##### 2.1.1.1 RRP criteria

- Histological diagnosis of RRP confirmed by pathology report from a CLIA-certified laboratory.
  - One of the following:
    - A Derkey anatomic score of 10 or greater (See Section 12.4) and a history of two or more endoscopic interventions in the last 12 months for control of RRP.
    - Pulmonary RRP with pulmonary disease that is measurable by computed tomography scan.
    - Tracheal involvement with RRP that has required either two or more endoscopic interventions in the last 12 months or a tracheostomy.
  - Greater than or equal to 18 years of age.
- 2.1.1.2 Able to understand and sign the Informed Consent Document.
- 2.1.1.3 Clinical performance status of ECOG 0 or 1. See section 12.1
- 2.1.1.4 Willing to undergo endoscopic evaluation with biopsies in compliance with this protocol.
- 2.1.1.5 No systemic therapy for RRP for four weeks prior to treatment.
- 2.1.1.6 Screening laboratory values must meet the following criteria and should be obtained within 14 days prior to first dose:
- WBC > 2000/ $\mu$ L
  - Neutrophils > 1500/ $\mu$ L
  - Platelets > 100  $\times 10^3$ / $\mu$ L
  - Hemoglobin > 9.0 g/dL
  - Serum creatinine < 1.5 x ULN or creatinine clearance (CrCl) > 30 mL/min (measured or calculated using the Cockcroft-Gault formula below):  
Female CrCl: 
$$\frac{(140 - \text{age in years}) \times \text{weight in kg} \times 0.85}{72 \times \text{serum creatinine in mg/dL}}$$
  
Male CrCl: 
$$\frac{(140 - \text{age in years}) \times \text{weight in kg} \times 1.00}{72 \times \text{serum creatinine in mg/dL}}$$
  - AST/ALT  $\leq$  2.5 x ULN; for subjects with documented metastatic disease to the liver, AST and ALT levels  $\leq$  5 x ULN
  - Total Bilirubin  $\leq$  1.5 x ULN
- 2.1.1.7 Sexually active subjects (men and women) and all subjects of reproductive potential must agree to use two methods of contraception: one highly effective and one other effective method for at least 28 days prior, throughout the avelumab treatment and for at least 60 days after avelumab treatment. Highly Effective Methods are defined as: Intrauterine device (IUD), hormonal (birth control pills, injections, implants), tubal ligation and partner's vasectomy; Other Effective Methods are defined as: latex condom, diaphragm and cervical cap.

- 2.1.1.8 Seronegative for HIV antibody. The experimental treatment being evaluated in this protocol depends on an intact immune system. Patients who are HIV seropositive can have decreased immune function and thus are likely less responsive to the experimental treatment.
- 2.1.1.9 Seronegative for hepatitis B antigen, positive hepatitis B tests can be further evaluated by confirmatory tests (Hep B DNA Quant, HBV Viral Load), and if confirmatory tests are negative, the patient can be enrolled.
- 2.1.1.10 Seronegative for hepatitis C antibody unless antigen negative. If hepatitis C antibody test is positive, then patients must be tested for the presence of antigen by Hep C RNA Quant, HCV Viral Load and be HCV RNA negative.
- 2.1.2 Exclusion criteria
  - 2.1.2.1 Any severe acute or chronic medical or psychiatric conditions including recent (within the past year) or active suicidal ideation or behavior, liver disease, lung disease (with the exception of what is specified in inclusion criteria in section **2.1.1.1**), or laboratory abnormalities that, in the opinion of the investigators, may increase the risk associated with study participation or study drug administration, impair the ability of the subject to receive protocol therapy, or interfere with the interpretation of study results and in the judgment of the investigator, would make the patient inappropriate for entry into this study. Patients with mild to moderate asthma or chronic obstructive pulmonary disease (COPD) well controlled with oral or inhaled medications are permitted to enroll.
  - 2.1.2.2 Subjects with active, known or suspected autoimmune disease. Subjects with vitiligo, residual hypothyroidism due to autoimmune condition only requiring hormone replacement, or psoriasis not requiring systemic treatment, are permitted to enroll.
  - 2.1.2.3 Subjects with a condition requiring systemic treatment with either corticosteroids (> 10 mg daily prednisone equivalents) or other immunosuppressive medications within 14 days of study drug administration. Inhaled, topical intranasal or intro-ocular steroids, and adrenal replacement doses <10 mg daily prednisone equivalents are permitted in the absence of active autoimmune disease.
  - 2.1.2.4 Prior organ transplantation, including allogeneic stem cell transplantation.
  - 2.1.2.5 Prior treatment with an anti-PD-1, anti-PD-L1, anti-PD-L2, anti-CTLA-4 antibody, or any other antibody or drug specifically targeting T-cell co-stimulation or immune checkpoint pathways.
  - 2.1.2.6 Patients who are receiving any other investigational agents
  - 2.1.2.7 Pregnant or breast feeding. Women of childbearing potential must have a negative pregnancy test at screening. Women of childbearing potential include women who have experienced menarche and who have not undergone successful surgical sterilization (hysterectomy, bilateral tubal ligation, or bilateral oophorectomy) or are not postmenopausal. Post-menopause is defined as amenorrhea  $\geq 12$  consecutive months. Note: women who have been amenorrheic for 12 or more months are still considered to

be of childbearing potential if the amenorrhea is possibly due to prior chemotherapy, anti-estrogens, ovarian suppression or any other reversible reason.

- 2.1.2.8 History of allergy to study drug components.
- 2.1.2.9 History of severe hypersensitivity reaction to any monoclonal antibody (Grade  $\geq$  3 NCI-CTCAE v 4.03), any history of anaphylaxis, or uncontrolled asthma (that is, 3 or more features of partially controlled asthma).
- 2.1.2.10 Clinically significant (i.e., active) cardiovascular disease: cerebral vascular accident/stroke (< 6 months prior to enrollment), myocardial infarction (< 6 months prior to enrollment), unstable angina, congestive heart failure ( $\geq$  New York Heart Association Classification Class II), or serious cardiac arrhythmia requiring medication.
- 2.1.2.11 Persisting toxicity related to prior therapy of Grade >1 NCI-CTCAE v 4.03; however, alopecia, sensory neuropathy Grade  $\leq$  2 or other Grade  $\leq$  2 AEs not constituting a safety risk based on investigator's judgment are acceptable.
- 2.1.2.12 Known alcohol or drug abuse.
- 2.1.2.13 Vaccination within 4 weeks of the first dose of avelumab and while on trial is prohibited except for administration of inactivated vaccines.

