#### 5.2.2 Definition of measurable disease

- Any papilloma that can be visualized via clinic-based endoscopy and assigned a score using the Derkay system
- Any papilloma that can be measured by imaging using RECIST 1.1 criteria.

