#### 5.2.3 Definition of disease response

##### 5.2.3.1 Complete Remission (CR)

All criteria must be met.

- No evidence of papillomas on physical exam and/or clinic-based flexible nasopharyngolaryngoscopy and/or tracheoscopy.
- No evidence of papillomas by exam under anesthesia (sedation or general anesthesia) with endoscopy and biopsies.
- Absence of disease by imaging if lesions are assessed by imaging.

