## **9 STATISTICAL CONSIDERATIONS**

The trial will be conducted using a Simon optimal two-stage design; the objective is to rule out a 5% complete response rate ( $p_0=0.05$ ) and target a 20% complete response rate ( $p_1=0.20$ ).

The design will use  $\alpha=0.10$  (10% chance of accepting a poor agent) and  $\beta=.10$  (corresponding to 90% power--and 10% chance of incorrectly rejecting a promising agent).

The first stage of accrual will consist of 12 evaluable patients. If 0/12 has a complete clinical response, then no further patients would be enrolled to that cohort. Should 1 or more patients in the first 12 have a complete response, then accrual would continue until a total of 37 evaluable patients have enrolled. If there are 1 to 3 complete responses in 37 patients, this would be considered unacceptably low, while if 4 or more patients have complete responses in 37 patients, then the results will be considered sufficiently promising for further evaluation. Under the null hypothesis (5% complete response rate), the probability of early termination is 54.0%.

It is anticipated that up to 2 patients per month may enroll onto this trial; thus, up to 2 years may be required to complete accrual. The trial would require up to 37 total evaluable patients; the accrual ceiling will be set at 40 patients to allow for a small number of inevaluable patients.

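### Complete response is defined only by absence of papillomas, and nothing requires a visible papilloma when dosing starts, so a surgical clearance can be counted as a response to avelumab

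*Combined protocol and SAP*

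**What the plan says.** **Entry.** Section 2.1.1.1 offers three alternative routes. The laryngeal route needs a Derkay anatomic score of at least 10 and a procedure history. The pulmonary route needs disease measurable on CT. The third is "Tracheal involvement with RRP that has required either two or more endoscopic interventions in the last 12 months or a tracheostomy", with no score or lesion minimum. Section 2.1.1.5 adds "No systemic therapy for RRP for four weeks prior to treatment" and is silent on surgery.

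**Contrary text.** Section 5.2 says the clinic-based score must be 10 or greater for eligibility, and section 1.2.4 describes that score as a condition for all patients. Section 5.2 also allows imaging-assessed patients who have no Derkay score at all.

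**Before dose 1.** Section 2.3 allows the baseline EUA to debulk lesions that threaten the airway. Study calendar footnote h places that EUA within 7 days before the first dose. Neither place says whether the baseline score is taken before or after debulking.

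**Response.** Section 5.2.2 defines measurable disease as "Any papilloma that can be visualized via clinic-based endoscopy and assigned a score using the Derkay system", or a lesion measurable on imaging, but no eligibility or analysis rule invokes it. Section 5.2.3.1 requires "No evidence of papillomas on physical exam and/or clinic-based flexible nasopharyngolaryngoscopy and/or tracheoscopy", a clear EUA with biopsies, and clear imaging where imaging is used. The first assessment is at week 6 (3.1.1).

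**Decision rule.** In section 9, "the objective is to rule out a 5% complete response rate" and "target a 20% complete response rate". Accrual stops at 0 CRs in 12 evaluable patients; otherwise it continues to 37, and 4 or more CRs are promising. Evaluable is not defined.

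**The concern.** Section 1.2.1 calls endoscopic debulking the mainstay of treatment, so many candidates will have had it recently. A tracheal patient cleared outside the study shortly before entry, or at the protocol's own baseline EUA, may have nothing visible at dose 1. If regrowth takes longer than six weeks, that patient is still clear at the first assessment and meets the CR definition whatever the drug did. The rule in 3.6.1 that removes patients given other RRP treatment operates only once they are on therapy, so it does not reach back before dose 1.

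With no control arm, such a patient cannot be separated from a true responder. The design is sensitive to small numbers: a single CR opens stage 2, and four in 37 decide the trial.

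**Working it through.** **1. Reproduce the plan (section 9: p0 = 0.05, p1 = 0.20, rule 0/12 then at least 4/37).**

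- Early termination at p0: 0.95^12 = 0.540, as stated.
- P(promising) = sum over x ≥ 1 of P(x CRs in 12) × P(at least 4 − x CRs in 25). At p = 0.05: 0.3413 × 0.1271 + 0.0988 × 0.3576 + 0.0173 × 0.7226 + 0.0022 × 1 = 0.093.
- The same sum at p = 0.20 gives 0.902.

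The design meets its stated alpha and power of 0.10 and 0.90. No sample-size figure is wrong.

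**2. Assumed inputs (the documents give none of these).**

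- Time to visible regrowth after clearance is exponential with mean m = 26, 13 or 6.5 weeks. The first is the average interval at the entry floor of two procedures a year (52/2); the others allow for earlier visible regrowth.
- One or two of the 37 patients are papilloma-free at dose 1 and are placed at random between the stages. They can be CRs only through persisting clearance. The other patients have the null 5% rate.
- The chance of still being clear at week t is q = exp(−t/m). Week 6 is the first assessment. Week 10 (6 + 4) applies if the confirmation at 4 weeks or more in 5.2.4 is required.

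**3. One such patient.** The patient falls in stage 1 with probability 12/37.

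- If that patient is a CR, P(promising) is 0.2679 (placed in stage 1) or 0.2053 (stage 2): (12/37) × 0.2679 + (25/37) × 0.2053 = 0.2256.
- If not, it is 0.0843 or 0.0876, averaging 0.0865.
- Overall: q × 0.2256 + (1 − q) × 0.0865. For m = 26 at week 6: 0.794 × 0.2256 + 0.206 × 0.0865 = 0.197.

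**4. Two such patients.** Both fall in stage 1 with probability 66/666, one in each stage with 300/666, and both in stage 2 with 300/666. Averaged over placement, P(promising) is 0.4499 if both are CRs, 0.2138 if one is, and 0.0798 if neither is. Overall: q² × 0.4499 + 2q(1 − q) × 0.2138 + (1 − q)² × 0.0798.

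| Clear until | m (weeks) | q | One patient | Two patients |
|---|---|---|---|---|
| Week 6 | 26 | 0.794 | 0.197 | 0.357 |
| Week 6 | 13 | 0.630 | 0.174 | 0.289 |
| Week 6 | 6.5 | 0.397 | 0.142 | 0.202 |
| Week 10 | 26 | 0.681 | 0.181 | 0.310 |
| Week 10 | 13 | 0.463 | 0.151 | 0.226 |
| Week 10 | 6.5 | 0.215 | 0.116 | 0.142 |

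The plan's own figure is 0.093. Every cell is above it and above the stated "10% chance of accepting a poor agent".

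**The case against.** **Current disease may be implied.** Tracheal involvement reads naturally as present involvement. Screening endoscopy is there to document disease, the baseline EUA collects papilloma tissue, and section 9 counts only evaluable patients. Together with the score of 10 in 5.2 and 1.2.4, this suggests the authors expected visible disease at entry. That expectation stands, but it is not a rule. The listed criteria are alternatives, the score requirement conflicts with them, evaluable is undefined, and even a score of 10 at screening precedes the debulking allowed at the baseline EUA.

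**There are safeguards.** CR needs a clear EUA with biopsies, final responses rest on blinded independent review, and 5.2.4 makes best response depend on confirmation. These establish that papillomas are absent, not why. The confirmation sits in a RECIST-style lesion table and 5.2.3.1 does not repeat it. Where it applies it lowers the figures, as the week 10 rows show, without bringing them under 10%.

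**The size is assumed.** This stands in full. The 26-week mean is an interval between procedures, not a time to regrowth, and section 1.2.4 describes aggressive disease, which favors shorter times.

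**A stronger reading of the washout.** A reader might infer that a patient given a local injection days before screening is plainly eligible. The documents do not support that. Section 1.2.1 mentions "local injection of anti-viral and antiangiogenic" agents among adjuvant systemic therapies tested in trials, none widely adopted, so their status under 2.1.1.5 is only ambiguous. The point here does not depend on it.

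**Conclusion.** The gap is real in the text as written. An absence-based CR, a tracheal route without a lesion minimum, no stated interval since debulking, and permitted debulking in the week before dose 1 together allow a patient with no visible papilloma at dose 1 to be counted as a CR. The exposure is greatest for tracheal patients. It is smaller for laryngeal patients, where baseline debulking is limited to lesions threatening the airway, and slight for pulmonary disease measured on CT.

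Under the stated assumptions and a true 5% CR rate, the chance of a promising result rises from 9.3% to about 14-20% with one such patient and 20-36% with two. If clearance must hold to week 10, the ranges are about 12-18% and 14-31%. These are illustrations. A reader might infer that the trial's true false-positive rate is 20-36%, or that the two-stage design is miscalculated; neither follows. The documents give no count of such patients and no regrowth times, and the design reproduces exactly.

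The change should be made, because the primary endpoint can otherwise credit the drug with a surgical result.

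**What to change.** 1. Define evaluable in section 9, for example: *a patient counts in the 12 and the 37 only if at least one papilloma meeting 5.2.2 is documented after any pre-dose debulking and before dose 1, at the end of the baseline EUA, at the pre-dose clinic endoscopy, or on baseline CT; other treated patients are reported separately.* The condition is fixed before any outcome is seen.
2. Reconcile 2.1.1.1 with 5.2 and 1.2.4 on whether the score of 10 applies to every route, and state whether the baseline score is taken before or after debulking.

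**Cost.** The wording relies on examinations already planned. The calendar lists a pre-dose clinic endoscopy, but 3.3.1 makes it conditional on clinical indication, so the end-of-EUA record is the firmer source where an EUA is done. Perhaps one or two treated patients would not count, against 40 − 37 = 3 spare places. The operating characteristics in section 9 are unchanged if 37 countable patients are reached.

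**Limit.** One remaining papilloma is enough to qualify, so a patient debulked to a single small lesion still counts. The change removes the case of no visible disease at dose 1, not every effect of earlier surgery.
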